6.3 Outcome Measures

Primary outcome. Percent weight loss from baseline to week 72 is the study's primary outcome. At week 72, participants in the stigma + BWL intervention are predicted to maintain their 9% reduction in initial weight, as compared to a significantly smaller 5% reduction in the BWL alone group. Duplicate measures of height (with a wall-mounted stadiometer; Veeder-Root, Elizabethtown, NC) will be obtained at screening, and weight (with a digital scale; Detecto, model 6800A) will be measured at screening, randomization (baseline), and at weeks 20, 46, and 72. Weight will also be measured at all group sessions. Percent weight loss from baseline to weeks 20 and week 46 will be assessed as secondary outcomes, along with categorical weight loss at weeks 72, 46, and 20 (loss of $\geq 5\%$ and $\geq 10\%$ of initial body weight at each time point). Participants in the BWL group are predicted to lose 8% of their initial weight at week 20. Participants in the stigma + BWL group are expected to lose 1% more of their initial weight (9%) at week 20 due to greater engagement in physical activity.

Secondary outcomes.

Physical activity. All participants will be given triaxial accelerometers (ActiGraph GT9X) to wear on their wrist for a 1-week period within 4 weeks of each assessment period (baseline and weeks 20, 46, and 72). Accelerometry has been used in numerous clinical trials,⁶²⁻⁶⁵ and the ActiGraph to be used in this study was adopted in the 5-year extension of the Look AHEAD study. Established activity counts will be used to identify thresholds of physical activity (sedentary, light, moderate, vigorous).⁶⁶ Self-reported physical activity will be assessed with the Paffenbarger Physical Activity Questionnaire⁶⁷ to obtain specific information on the types of activity participants engage in, and a brief questionnaire used in prior studies⁶⁸ to collect data on sedentary behavior. Self-efficacy will be assessed with the Self-Efficacy for Exercise Scale⁶⁹ Exercise Outcome Expectations and Barriers Scale (perceived barrier items only),⁷⁰ and Weight and

Lifestyle Efficacy (WEL),⁷¹ which measure individuals' confidence in their ability to overcome barriers to exercising and controlling their weight. Greater physical activity by objective and self-report assessment is expected in the stigma + BWL intervention vs. BWL alone group at weeks 20, 46, and 72. Based on prior research,¹³ we predict that participants in the stigma + BWL group will engage in approximately 250 min/wk of physical activity at week 72, as compared to approximately 150 min/wk in the BWL alone group, thus contributing to the 4% difference in weight loss at week 72.

Cardiometabolic risk. Blood pressure, waist circumference, and blood samples (measures: triglycerides, cholesterol, and glucose) will be obtained at screening and weeks 20 and 72 to assess changes in cardiometabolic risk factors, particularly in the components and diagnosis of metabolic syndrome. Blood pressure also will be assessed at randomization. Blood pressure will be measured using an automated Dinamap monitor (Johnson & Johnson, XL model 9300) at three, 1-minute intervals after \geq 5 minute rest, using measures described previously.⁷² Waist circumference will be measured (to the nearest 0.1 cm) in duplicate with flexible tension-controlled measuring tape midway between the iliac crest and lowest rib. Blood samples will be drawn after an overnight fast to obtain plasma glucose levels and a lipid panel (triglycerides and HDL cholesterol), along with inflammatory markers of cardiometabolic risk (e.g., C-reactive protein). Samples will be sent to Quest Diagnostics (Horsham, PA) for analysis. Additionally, the study nurse practitioner or physician will review current medication use. Improvements in triglycerides, HDL cholesterol, and glucose are expected at week 20 in both treatment groups because of acute weight loss and calorie restriction. Due to higher levels of physical activity, greater weight loss, and reduced WBI, the magnitude of improvement is expected to be greater in the stigma + BWL intervention vs. BWL alone group at week 72.

Weight bias coping and internalization. Participants will complete the WBIS (described previously) at screening and weeks 20, 46, and 72. In addition to scoring this measure on its continuous scale, the percentage of participants who do and do not meet the eligibility criterion cutoff score (4 or above) will be calculated at weeks 20, 46, and 72, as a measure of "remission" from elevated WBI. Participants will also complete additional measures of stigma, quality of life, stress, and depression at randomization and all subsequent assessment times. Stigma questionnaires will include the Weight Self-Stigma Questionnaire (WSSQ; an alternative measure of WBI),⁷³ Fat Phobia Scale (a measure of stereotype endorsement),⁷⁴ and the Everyday Discrimination Scale (an assessment of unfair treatment in daily life for a variety of reasons, including weight).⁷⁵ The WBIS, WSSQ, Fat Phobia Scale, and Everyday Discrimination Scale are widely used and well validated.^{37,76-81} Additionally, an assessment of weight stigma coping strategies⁸² will be completed to assess the frequency with which participants engage in adaptive and maladaptive behaviors (e.g., exercising more vs. avoiding physical activity) in response to weight stigma. At baseline only, participants will complete the Weight Stigma Timing of Life Questionnaire to assess their history of weight-stigmatizing experiences, and the Adverse Childhood Experience Questionnaire to assess experiences of childhood trauma.⁸³ Participants will also complete the Impact of Weight on Quality of Life Questionnaire-Lite (IWQOL),⁸⁴ which contains five subscales that include items assessing distress due to weight-stigmatizing situations and weight-based discrimination. Participants will complete the Perceived Stress Scale (PSS)⁸⁵ to determine self-reported daily stress, the Questionnaire for Eating and Weight Patterns (QEWP)⁸⁶ to assess disordered eating, and the Patient Health Questionnaire (PHQ-9)⁸⁷ to assess

symptoms of depression. Participants will complete the Body Appreciation Scale⁸⁸ to assess changes in body positivity. Additionally, participants will complete a brief questionnaire assessing the frequency with which they self-monitor their weight and eating (along with food records which will be collected from participants at all group meetings to assess days of recorded food intake and activity), and treatment acceptability will be assessed at weeks 20 and 72. Participants in the stigma + BWL intervention group are predicted to show greater reductions in all measures of stigma and distress than participants in the BWL group at weeks 20, 46, and 72.

6.4 Safety Measures

Risks

The risk of adverse medical or psychiatric events should be minimized by the careful screening procedures to be used. The principal risks during the group lifestyle modification program include:

Risk of gallstones. Rapid weight loss may increase the risk of gallstones. The risk of gallbladder disease will be reduced by limiting weight loss to no more than 3 pounds per week for 4 consecutive weeks. Weight loss will be monitored at all group sessions. Patients will be asked to slow or stop their weight loss if there are concerns about the rate of their weight loss.

Blood draw. Risks of drawing blood include pain, bruising at the puncture site, swelling, feeling faint or lightheaded, and rarely infection.

Psychological distress. Participants may become distressed by learning about and discussing their experiences with weight-based discrimination and stigma.

Confidentiality and loss of privacy. All efforts will be made to protect participant confidentiality and privacy. We cannot guarantee total privacy. Personal information may be given out if required by law.

Ongoing medical visits and safety measures

A physician/nurse practitioner will be available if participants notice any side effects of weight loss. Participants who lose 15% or more of their initial body weight may be advised to inform their PCP of their weight loss, particularly if taking medications that may need to be adjusted due to weight loss (e.g., anti-hypertensive medications). Participants who report significant depression or emotional distress will be evaluated by the study's psychologist or psychiatrist and referred to their PCP for further evaluation and treatment. Participants will be referred to their PCP if their mood is significantly disrupting their normal function (as reflected by symptoms that include feeling blue, not enjoying usual activities, trouble sleeping or concentrating, or having thoughts of dying or harming oneself).

7. STATISTICAL ANALYSIS

Sample size calculation

Using a sample size equation for longitudinal clustered samples,⁸⁴ a power analysis was conducted for the **primary outcome: percent weight change at week 72**. Estimated group means, attrition rate, intraclass correlation (ICC), and variances were derived from data from prior studies

conducted at our Center.⁷² Specifically, we predict a 72-week weight loss of 9% in the stigma + BWL group and 5% in the BWL group, with expected standard deviations of 7%.⁷² Based on these estimates, a baseline sample size of 104 participants (52 per group), assuming a 20% attrition rate, an ICC of .80, and 4 assessment points, will give us 80% power to detect a between-treatment group difference at week 72 of 4% (effect size: 0.57) to be significant at alpha = 0.05. The power analysis was conducted using PASS v14. All secondary outcomes will be considered exploratory and will provide valuable findings that will help to inform larger studies. This study has not been powered to detect differences in changes in physical activity, cardiometabolic outcomes, or psychosocial variables.

Analysis plan

Data quality and integrity will be checked by assessing the data for missing and out-of-range values with basic statistical procedures, including univariate statistics and visual graphical displays (e.g., scatter plots). We will investigate all questions of data quality and integrity prior to performing any statistical modeling. To test the adequacy of randomization, preliminary analyses will include a comparison of all participant demographic and baseline characteristics by randomized treatment groups (t-tests or Wilcoxon rank sum tests for continuous variables and Chi-Square test or Fisher's Exact test for categorical data). If imbalances are observed, the relevant variables will be included as covariates in the final analyses.

All data will be analyzed with a modified intention-to-treat principle. Participants who attend at least one group meeting (i.e., receive a dose of treatment) will be included in the analyses; participants who do not attend a single group meeting will not be included in the analyses. Analyses will be two-tailed with a significance level of 0.05, and will be conducted using SPSS version 24.0 or SAS version 9.4. To assess the primary outcome of percent weight change by treatment group, a mixed effects model will be fit with Treatment Group (*stigma+BWL, BWL*) as a between subjects factor and Time (*Weeks 20, 46, 72*) as a categorical within-subjects factor. We will use the group x time interactions with the time main effect to estimate and test treatment group differences at each time point, with the 72-week time point as our primary test. In fitting a mixed effects model with residual maximum likelihood (REML), a variance-covariance structure must be selected. The criteria for selecting the best form of the variance-covariance structure will be based on criteria such as the Akaike's Information Criterion (AIC). We will include as baseline covariates any variables that differ significantly between the treatment groups at baseline and show significant relationships with the outcome. The results from the mixed model will be summarized by mean(SE) for each treatment group at each time point. Residual analyses will be conducted to check for outliers and influential points and violations in the normality assumption. If violations are detected, variance-stabilizing transformations will be considered. Logistic regression will be used to test for between-group differences in categorical weight loss ($\geq 5\%$ and $\geq 10\%$ of initial body weight) at weeks 72, 46, and 20.

The second aim of assessing changes in physical activity and self-efficacy, and the secondary aims of comparing changes in cardiometabolic risk factors and psychological well-being (including WBI), will be analyzed using the same methods as described above for the mixed effects model used for the primary aim. Changes in all outcomes will be summarized by mean(SE) for each treatment group at each time point. Logistic regression will be used to test for between-group

differences at weeks 20, 46, and 72 in the percentage of participants who have remitted from elevated WBI, as indicated by no longer having a score of 4 or above.

This study will consider death, pregnancy, bariatric surgery, amputation, and other major medical events or procedures that require a participant to terminate treatment as "censoring events." For primary analyses, participants experiencing these events will be censored at the last measured weight before the event occurred. As discussed above, the primary analysis techniques being employed (i.e., linear mixed models) can accommodate incomplete participant response profiles, so these participants will still be included in the analyses. Additional sensitivity analyses may be conducted in which data will be censored due to other factors that directly affect weight (e.g., change of medication that affects weight, receipt of additional weight-related treatment, change in smoking status, or other major medical changes that occur within 3 months of an assessment visit).

Additional analyses may be conducted to explore potential effects of cohort, time of group meeting, and group leader on weight loss and changes in WBI. Analyses may also explore potential differences in attendance between groups and the effects of attendance on weight loss and changes in WBI.

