4. STUDY DESIGN

4.1 General Design

This is a randomized controlled trial to test the effects on long-term weight loss of a novel stigma-reduction intervention combined with standard BWL treatment, as compared to BWL alone. Participants will be a total of 104 men and women seeking weight loss, ages 18 years and older, with a body mass index (BMI) of 30 kg/m² or above (or 27 kg/m² or above with an obesity-related comorbidity), a history of experiencing weight bias, and elevated levels of WBI. Participants will attend a screening visit in which they will complete a behavioral evaluation with a psychologist and a medical history that will be reviewed by a nurse practitioner or physician. Questionnaires assessing experiences and internalization of weight bias, with confirmation by interviewer assessment during the behavioral evaluation, will be used to determine whether participants meet criteria for having high levels of WBI. Eligible consenting participants will be randomly assigned to the standard BWL intervention (n = 52) or the stigma + BWL intervention (n = 52). All participants will attend weekly, 90-minute group meetings for 20 weeks (20 visits). In the stigma + BWL treatment group, beginning at week 5, 60 minutes will be devoted to BWL and 30 minutes to weight stigma. In the standard BWL treatment group, the additional 30 minutes will be devoted to sharing recipes and food preparation tips. Following 20 weeks of weight loss treatment, participants will attend group meetings focused on weight loss maintenance, monthly from weeks 21-46 (6 visits), and every-other-month from weeks 47-72 (3 visits). Maintenance sessions in the stigma + BWL group will continue to incorporate discussion of WBI and stigma-related barriers to physical activity. Assessments – which include questionnaires, blood draws, and measurements of body weight and physical activity – will occur at baseline and weeks 20, 46 (no blood draw this week), and 72. Weight will be measured at every group meeting for clinical purposes.

Other Therapy:

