Participants will be expected to attend 4 assessment visits throughout the course of the study: at baseline, week 20, week 46, and week 72 (or within 4 weeks of each assessment period). Three of these assessment visits (baseline, week 20, and week 72) will include a fasting blood test, which will include a comprehensive metabolic panel (CMP), lipid panel, insulin, high sensitivity C-reactive protein (hs-CRP), and hemoglobin A_{1c}. These tests will require approximately 34 mls of blood. Blood pressure, pulse, and waist measurement will also be measured at these outcome assessment visits, and weight will be measured at all assessment visits.

Participants will also be asked to monitor their physical activity and complete questionnaires at baseline, week 20, week 46, and week 72. Questionnaires will be completed online or administered/returned via mail or at scheduled group sessions. Accelerometers will be administered at scheduled group sessions or assessment visits and returned in person or by mail, with an accompanying brief interview to assess activity over the past week (in person or by phone).

Adjustments to outcome assessment visits due to COVID-19. During the pandemic, in-person assessment visits will be replaced with remote assessments whenever possible. Specifically, all week 46 assessment visits will be conducted remotely for the duration of the pandemic. If permitted by the city, institution, and funding sponsor, week 20 and week 72 assessment visits will be offered in-person, in order to allow for the measurement of blood pressure and a fasting blood test. All local and institutional safety regulations will be followed when conducting in-person visits. Participants with safety concerns or other barriers that prevent them from attending in-person assessment visits will be offered remote assessments without penalty.

Remote assessment visits will be scheduled during the morning and will involve a brief phone call with the study coordinator, measurement of weight (and for weeks 20 and 72, measurement of waist circumference), monitoring of activity with an accelerometer device, and completion of online questionnaires. As described above, all participants will be sent an EatSmart Precision Digital Scale (with a tape measure included in the package). For remote assessments, participants will be asked to use the EatSmart scale to weigh themselves in duplicate, in kilograms, in the morning before eating anything. Participants will be asked to send

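### The primary mixed model has response rows only at weeks 20, 46 and 72, so an attender with no weight at any of these visits is not analysed, although section 7 says attenders are included

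*Combined protocol and SAP*

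**What the plan says.** All references are to the combined protocol and SAP.

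- **Population (section 7, Analysis plan).** The principle is modified intention-to-treat: "Participants who attend at least one group meeting (i.e., receive a dose of treatment) will be included in the analyses". Only people who never attend a meeting are left out.
- **Outcome (section 6.3).** "Percent weight loss from baseline to week 72 is the study's primary outcome".
- **Primary model (section 7).** A REML mixed model with treatment group and "Time (*Weeks 20, 46, 72*) as a categorical within-subjects factor". The week-72 group difference is the primary test.
- **Censoring events (section 7).** For events such as pregnancy or bariatric surgery, "participants experiencing these events will be censored at the last measured weight before the event occurred". The text adds that linear mixed models "can accommodate incomplete participant response profiles, so these participants will still be included in the analyses".
- **Meeting weights.** Section 4.1 states: "Weight will be measured at every group meeting for clinical purposes". Section 6.3 also mentions session weights in its primary-outcome paragraph, but section 7 gives them no role in the model.
- **Timing.** Meetings are weekly for the first 20 weeks (section 4.1). Assessment visits may fall within 4 weeks of their nominal time, and remote weights are allowed during the pandemic (section 6.2).

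**The concern.** The inclusion rule depends on attending one meeting, which can happen in week 1. The model's first response is at week 20. A participant can therefore attend many meetings, leave, and have no value that the model can use. A mixed model accommodates an incomplete profile, but not an empty one. For the same reason, a person censored before week 20 at a weight taken in a meeting has no time level for that weight.

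Two things are at stake. The result would be reported as covering everyone who received a dose of treatment when it does not. And if early leaving differs between arms and goes with poorer early loss, the week-72 difference is biased, although that early loss was measured and is on file.

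**Working it through.** **1. The plan's own sample size.** Inputs from section 7: difference 4, SD 7, two-sided alpha 0.05, power 80%, ICC 0.80, m = 4 assessments, 20% attrition. With the repeated-measures formula,

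n per arm = 2 × [7 × (1.960 + 0.842) / 4]² × [1 + (m − 1) × 0.80] / m.

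For m = 4 the last factor is 3.4/4 = 0.85 and n = 40.86, so 41. Then 41/0.8 = 51.25, so 52 per arm and 104 in total, which matches the plan. With the model's three time levels the factor is 2.6/3 = 0.867, giving 42, then 53 per arm and 106 in total.

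**2. Precision.** If the whole 20% allowance had no modelled weight, 0.8 × 52 = 41.6 per arm would remain. Power by the same formula is 80.7% (m = 4) or 79.9% (m = 3). Power is not the problem.

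**3. What the model does with an empty profile.** A participant's likelihood contribution is the density of the observed responses. With none observed there is no contribution. As a check, one simulated trial of 104 was fitted after all three values were blanked for 10 people. The model used 94 people. The estimate (−5.341) and standard error (1.341) were identical to those after deleting the 10 outright. A baseline row on the percent-change scale would not help, because it is 0 for everyone.

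**4. How many.** The documents do not say. Assumed shares of 0, 5, 10 and 20% of attenders give 0, 5.2, 10.4 and 20.8 of 104.

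**5. Size of the bias, by simulation.** The true difference is 4.0, with 52 per arm and 4,000 trials per scenario. The following are assumptions, not figures from the plan: week-8 loss 4.0% versus 4.2%, SD 2.2, correlation 0.45 with week 72, and odds of early dropout multiplied by 2.7 to 4.5 per SD of poorer early loss. Paired figures are for two strengths of that dependence.

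| Early dropout, BWL / stigma + BWL | Planned model, mean week-72 difference | With a week-8 level added |
|---|---|---|
| about 16% / 6% | 3.72 and 3.66 | 3.99 and 3.98 |
| about 6% / 16% | 4.24 and 4.30 | 3.98 and 3.97 |
| about 11% / 11% | 3.99 | 4.00 |

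Other assumed correlations gave 3.66 to 3.73 and 4.32 to 4.36 for the planned model in the two unequal cases. The shift is thus about 0.2 to 0.4 points. With a standard error of about 1.5 that is 0.2/1.5 = 0.13 to 0.4/1.5 = 0.27 standard errors. At 12% versus 8% it is about 0.1 to 0.2.

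**6. How much an early level recovers.** The week-8 column is favourable by construction, because dropout was made to depend on week-8 loss. A week-4 level behaves as follows:

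- Dropout depends on week-4 loss: the planned model gives 3.76, or 4.18 to 4.29 with the arms reversed. The week-4 level restores 3.97 to 4.03.
- Dropout depends on week-8 loss (assumed correlations of week 4 with week 8 and week 72 of 0.8 and 0.30): the week-4 level gives 3.91, 3.83, 4.14 and 4.18. The remaining shifts are −0.09, −0.17, +0.14 and +0.18, against about −0.2, −0.3, +0.3 and +0.4 without it. About half the bias goes. With correlations of 0.6 and 0.25, about a third goes.

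**The case against.** The strongest reply is that this is a wording slip with a small and speculative effect. The documents give neither the timing of dropout nor any arm difference. The 16% versus 6% scenario stacks several assumptions and still moves the estimate by well under one standard error. The 4-week visit windows and remote weights shrink the affected group. All of this stands and limits the weight of the point. It does not remove the mismatch, because smaller is not zero and nothing else in section 7 brings these people in.

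A second reply is that the bias is really a missing-at-random question. That is largely right for the bias: it arises because leaving depends on early loss, which the model does not contain. The statement of who is analysed is wrong whatever the missingness mechanism.

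Third, a reader might infer that the analysed set is settled entirely after the arms diverge. The documents do not support this. Session content differs only from week 5 (sections 4.1 and 6.2), so people who leave in weeks 1 to 4 do so before it differs. Nor is the censoring statement wrong for everyone: it fails only for those with no modelled weight.

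Fourth, one might propose making baseline the first response, on the log-weight scale with a common baseline mean, so that everybody formally enters the likelihood. That changes the estimand: 0.91/0.95 = 0.958, a 4.2% relative difference rather than 4.0 points. It also corrects little by itself. In simulation it gave 4.21 with no dropout and 4.01, 3.89, 4.52 and 4.61 in the four unequal scenarios, which are shifts of −0.20, −0.32, +0.31 and +0.40.

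**Conclusion.** The mismatch is certain from the text: section 7 promises every attender, and the model delivers attenders with at least one weight at week 20, 46 or 72. Its numerical effect is uncertain. It is zero if early dropout is equal between arms, and moderate at most under the unequal scenarios in the working, all of which rest on assumed dropout rates and correlations. The direction depends on which arm loses more people early.

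Two stronger readings should be resisted. One is that the trial is underpowered because of this; the attrition allowance covers it. The other is to assume that every omitted attender lost nothing. That would make the all-attender difference 0.9 × 9 − 0.9 × 5 = 3.6 with 10% omitted in each arm, or 0.8 × 9 − 0.9 × 5 = 2.7 with 20% omitted from stigma + BWL and 10% from BWL. The documents give neither the number omitted nor their outcomes. The same assumption could be made about people who leave after week 20, so it does not measure this defect.

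**What to change.** 1. Keep percent weight change as the outcome and the week-72 contrast as the primary test. Add one or more time levels before week 20, for example about weeks 4, 8 and 12, using weights already taken at group meetings, with windows defined in advance. Several levels are better than week 4 alone, which recovers only part of the bias if leaving depends on later loss.
2. Correct both inclusion statements in section 7 to say that the model includes attenders with at least one modelled post-baseline weight. This is needed even with the added levels, since someone who leaves before the first window still has no row.
3. Report the number of attenders excluded from the model, by arm.

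The cost is SAP wording and a larger model, with no new data collection. An unstructured covariance matrix grows from 3 × 4/2 = 6 parameters to 4 × 5/2 = 10 with one added level, or 6 × 7/2 = 21 with three. Session weights are taken for clinical purposes and, during COVID-19, are self-reported by email from home scales (section 6.2), so the SAP should state how they are handled. If the sponsor prefers to keep the three-level model, items 2 and 3 are the minimum.
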